11.1. Participant Completion

Completion of the study will be defined as reaching the Week 117 (or equivalent) visit and participating in at least 90% of CFRU visits.

11.2. Participant Stopping Rules and Withdrawal Criteria

Participants may be prematurely terminated from the study for the following reasons:

- 1. The participant elects to withdraw consent from all future study activities, including follow-up.
- 2. The participant is "lost to follow-up" (i.e., no further follow-up is possible because attempts to reestablish contact with the participant have failed).
- 3. The participant dies.
- 4. The Investigator no longer believes participation is in the best interest of the participant.
- 5. Individual safety stopping rules
 - a. Missing >7 consecutive days of OIT therapy (e.g., concurrent illness such as gastroenteritis)
 - b. Missing >3 consecutive days of OIT therapy on 3 occasions without consulting with study staff
 - c. Anaphylaxis resulting in hypotension, neurological compromise or mechanical ventilation secondary to OIT dosing or any peanut food challenge
 - d. Any allergic reaction to study drug requiring more than 2 doses of epinephrine due to single event
 - e. The subject develops biopsy-documented eosinophilic esophagitis (EoE) with symptoms or other eosinophilic gastrointestinal disease
 - f. Any subject deemed to have severe allergic reactions and who receives aggressive therapy (e.g., IV fluid resuscitation, mechanical ventilation, repeated doses of epinephrine for a life threatening reaction) at any time should be discontinued from further therapy.
 - g. Other circumstances including, but not limited to, the following:
 - i. Poor control or persistent activation of secondary atopic disease (e.g., AD, asthma)
 - **ii.** Started on beta-blockers, or other prohibited medications, with no alternative medications available per the prescribing physician
 - iii. Pregnancy

11.3. Participant Replacement

Subjects who initiate therapy (i.e., who do not fail the Initial Dose Escalation Day AND also initiate home dosing) in this trial will not be replaced.

11.4. Follow-up after Early Study Withdrawal

Subjects who prematurely discontinue treatment with OIT may remain in the study until end of study visit at week 156. All willing subjects will be followed every 13 weeks for the duration of the study to monitor safety and efficacy parameters. These visits will include skin testing and a blood draw for mechanistic studies.

If the subject refuses this follow-up, or begins and then elects to discontinue the follow-up, they will be asked to come in for a final study visit consisting of a physical assessment, skin test, blood draw, review of their Food Allergy Action Plan, and instructions to discontinue any OIT dosing.

11.5. Study Stopping Rules

During the course of the study, if the investigator or the NIAID Medical Officer discovers conditions that indicate that the study should be discontinued, an appropriate procedure for stopping the study pending DSMB review will be instituted, including notification of the FDA and IRB.

If any of the stopping rules listed below are met, study enrollment will be suspended, the Initial Dose Escalation days will be suspended, dose escalation during Build-up will be stopped, and all enrolled participants will remain on their current dose pending expedited review of all pertinent data:

- Any death related to peanut OIT dosing
- One case of severe and prolonged anaphylaxis that does not respond to 3 doses of epinephrine, or that includes intubation and that is related to peanut dosing or to oral food challenge.
- More than 2 cases of hypotension related to peanut dosing or to oral food challenge.
- More than 3 participants require more than 2 injections of epinephrine for anaphylaxis during a single dosing event of the peanut product.
- More than 3 of either of the following events:
 - Severe adverse event, other than anaphylaxis, related to investigational product or
 - Eosinophilic esophagitis with clinical symptoms and confirmatory biopsy findings

12.Safety Monitoring and Reporting

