12.2. Definitions

12.2.1. Adverse Event (AE)

Any untoward or unfavorable medical occurrence associated with the subject's participation in the research, whether or not considered related to the subject's participation in the research (modified from the definition of adverse events in the 1996 International Conference on Harmonization E-6 Guidelines for Good Clinical Practice) (from OHRP "Guidance on Reviewing and Reporting Unanticipated Problems Involving Risks to Subjects or Others and Adverse Events (1/15/07)" http://www.hhs.gov/ohrp/policy/advevntguid.html#Q2)

For this study, an adverse event will include any untoward or unfavorable medical occurrence associated with:

• Study therapy regimen:

Home OIT Dosing

- Food allergy episodes in response to home dosing that are objective Grade 1 or 2 by Modified Bock's Criteria (**APPENDIX 4**) will be recorded on the paper AE CRFs and graded by CTCAE v 4.03 criteria.
- Food allergy episodes in response to home dosing that are Grade 3 by Modified Bock's Criteria (APPENDIX 4) or that are classified as SAEs defined in Section 12.2.3 below will be recorded on the AE/SAE CRF as appropriate and graded by CTCAE v 4.03 criteria.
- Study mandated procedures:

For the procedures below, clinical situations are listed that are considered to be outside the normal range of outcomes and will be recorded as Adverse Events. These situations do not limit an investigator from recording and reporting any other events, associated or not with these procedures as AEs.

Allergen Skin Testing

- Prolonged (>24 hours) itching at test site
- Swelling (> 10 cm) at site of test lasting more than 24 hours
- Nasal allergic symptoms within 30 minutes from the procedure
- Fainting /Vasovagal event within 30 minutes from the procedure

Phlebotomy

- Bruising at phlebotomy site >5 cm with onset within 24 hours of procedure
- Erythema at phlebotomy site >5 cm with onset within 24 hours of procedure
- Infection at phlebotomy site
- Fainting /Vasovagal event within 30 minutes from the procedure

Double-Blind Placebo Controlled Food Challenges

- During DBPCFCs, reactions will be recorded. DBPCFC material is not considered study drug, and as such, reactions will be recorded and reported separately. GI biopsies

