12.8.2.2. Ad hoc DSMB Reviews

In addition to the pre-scheduled data reviews and planned safety monitoring, the DSMB may be called upon for *ad hoc* reviews. The DSMB will review any event that potentially impacts safety at the request of the NIAID Medical Monitor. In addition, the following events will trigger an *ad hoc* comprehensive DSMB Safety Review:

- Any death that occurs in the study.
- The occurrence of the same unexpected SAE in 3 or more of the study participants who have received a study treatment.

After review of the data, the DSMB will make recommendations regarding study conduct and/or continuation.

12.8.2.2.1. Temporary Suspension of Enrollment and/or Drug Dosing for *ad hoc* DSMB Safety Review

A temporary halt in enrollment and/or drug updosing will be implemented if an *ad hoc* DSMB safety review is required per the criteria outlined in section 12.8.2.2. above.

In the event of a study halt for DSMB review, subjects in the screening phase will continue to undergo screening procedures unless the review was triggered by events related to screening.

Subjects already receiving therapy will remain on study treatment at their current tolerated dose.

Based on the outcome of the DSMB review, the consent and/or assent forms may be revised. Upon approval of these revisions by the IRB, all subjects who have previously provided informed consent for the study and are affected by the new information will be re-consented.

13.Statistical Considerations and Analytical Plan

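### The death stopping rule in 11.5 and the synopsis omits oral food challenge, so a narrow class of challenge deaths does not trigger the full mandatory halt

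*Protocol*

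**What the plan says.** Section 11.5, repeated in the synopsis, sets rules that remove discretion. If one is met, "study enrollment will be suspended, the Initial Dose Escalation days will be suspended, dose escalation during Build-up will be stopped", and everyone already enrolled is held at the current dose pending expedited review. The first three rules differ in scope:

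- Death: "Any death related to peanut OIT dosing".
- Severe, prolonged anaphylaxis, one case: failing 3 doses of epinephrine, or one "that includes intubation and that is related to peanut dosing or to oral food challenge".
- Hypotension: "More than 2 cases of hypotension related to peanut dosing or to oral food challenge".

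The remaining rules concern repeated epinephrine use during dosing of the peanut product, severe events related to investigational product, and eosinophilic esophagitis. Section 12.2.1 states that "DBPCFC material is not considered study drug" and has challenge reactions reported separately.

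A second layer sits in 12.8.2.2. There, "Any death that occurs in the study" triggers an ad hoc DSMB review. Under 12.8.2.2.1, "A temporary halt in enrollment and/or drug updosing will be implemented", treated subjects stay at their tolerated dose, and subjects in screening carry on unless an event related to screening prompted the review.

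**The concern.** The protocol treats the food challenge as its own source of harm and names it in two adjacent rules, but not for the gravest outcome. The death rule cannot comfortably be stretched to cover it. Challenge material is declared not to be study drug, and if dosing already included challenges, the extra words in the next two rules would be redundant.

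The ordering is therefore uneven: a non-fatal challenge reaction with intubation forces the full halt, while some challenge deaths do not. Section 5.2 of the protocol acknowledges that challenge reactions can be life-threatening. At stake is whether all the protective suspensions follow automatically after such a death.

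**Working it through.** There is no planned figure to reproduce, since the point concerns wording. The test case is one death caused by an oral food challenge, with no intubation, no anaphylaxis that failed 3 epinephrine doses, and fewer than 3 hypotension cases in the study so far. An illustration is a collapse that ends before a third dose is given.

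**Step 1. Each 11.5 trigger against the test case** (5 bullets; the last holds two events, giving 6 triggers)

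| Trigger | Names challenge? | Met? | Reason |
|---|---|---|---|
| Death | No | No | Limited to OIT dosing |
| Anaphylaxis | Yes | No | Neither feature present, by construction |
| Hypotension | Yes | No | More than 2 means at least 3 cases |
| Epinephrine | No | No | More than 3 means at least 4 participants, in a product dosing event |
| Severe adverse event | No | No | At least 4 events, related to investigational product |
| Eosinophilic esophagitis | No | No | Different event |

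Result: 0 of 6 met. Of the 5 bullets, 2 name the challenge. By contrast, one survivor of a severe, prolonged challenge anaphylaxis with intubation meets the second trigger alone.

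**Step 2. What 12.8.2.2 and 12.8.2.2.1 still require.** The any-death trigger is met, so DSMB review and some halt are compulsory.

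| Activity | 11.5 halt | 12.8.2.2.1 halt |
|---|---|---|
| Enrollment | Suspended | One of two items joined by *and/or* |
| Initial Dose Escalation days | Suspended by name | Not named in the sentence |
| Build-up escalation | Stopped | Treated subjects held at tolerated dose |
| Screening procedures | Not named | May not rely on the permission to continue if a screening event caused the review |

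Build-up dose is held either way. The difference is enrollment, which can remain open if updosing is what is halted, and first-dose days, which are not named.

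**Step 3. Which challenges this concerns.** Assume 52-week years and that the last subject completes Week 156 within the 5-year study.

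- Study length: 5 × 52 = 260 weeks.
- Latest Initial Dose Escalation day: 260 − 156 = week 104.
- Earliest on-study challenge: Week 104 after the first such day.
- Overlap of on-study challenges with pending first-dose days: 104 − 104 = 0 weeks, or about 2 if the earliest Week 104 challenge uses the 2-week window in Appendix 1.

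So the practical case is mainly the screening challenge. There is one per enrolled subject, 120 × 1 = 120, plus an unstated number in screen failures, less any done under another protocol as 8.2 allows. The documents give no event rate, and none is assumed here.

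**Step 4. Effect of the change.** With oral food challenge added to the death rule, the test case meets the first trigger and the full 11.5 halt follows.

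**The case against.** The strongest reply is that the sections are layered and do not conflict: 11.5 handles product signals, and 12.8.2.2 catches every death. Review is compulsory, a halt is compulsory, and treated subjects stay at their dose. The opening of 11.5 also obliges a stopping procedure once the investigator or the NIAID Medical Officer finds conditions that call for one, and 12.5.1 sends serious events to the Medical Monitor within 24 hours. Challenges are physician-supervised, with at least 2 hours of observation. Many fatal challenge reactions would meet the anaphylaxis rule anyway.

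All of this stands, and it is why the point is small. It does not close the gap. Finding that conditions call for a stop is a judgement, and a halt of one item satisfies 12.8.2.2.1.

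A reader might infer more than the text supports:

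- *That the trial could carry on unchecked after a challenge death.* It could not, because 12.8.2.2 applies to any death.
- *That screening challenges would continue after a screening-challenge death.* The exception in 12.8.2.2.1 withdraws that permission. On this activity it is stricter than 11.5, which does not mention screening procedures.
- *That first doses would certainly go ahead.* The heading of 12.8.2.2.1 reads "Temporary Suspension of Enrollment and/or Drug Dosing", and a purposive reading would probably stop them. An enrollment halt would also stop them if enrollment means entry after screening, as in 3.1 and 8.2. Section 8.1 instead counts subjects as enrolled at consent, so the text leaves this open.
- *That 12.8.2.2.1 needs rewriting.* Its flexible wording permits a proportionate response to an unrelated death. Requiring every suspension there would force a full halt after, say, an accident.

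**Conclusion.** The point holds as a minor drafting inconsistency in the safety rules. After a challenge death of the kind tested, the protocol guarantees DSMB review and some halt. It does not guarantee that enrollment, Initial Dose Escalation days and build-up escalation are suspended together, although it guarantees exactly that after one survivable intubated challenge reaction.

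This rests on reading OIT dosing as excluding challenges, which 12.2.1 and the neighbouring rules support. The timeline in the working rests on its stated assumptions, but the textual conclusion does not depend on it. No endpoint, analysis, power or error rate is affected.

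**What to change.** In 11.5 and in the synopsis, extend the death rule by adding *or to oral food challenge* after its present wording, matching the two rules that follow it. Leave 12.8.2.2.1 unchanged.

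The cost is a few words in two places, with no added visits, staff or patients. The change brings the full 11.5 halt into play after a challenge death. It does not by itself suspend further challenges, because the 11.5 halt does not list them.

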12.1. Overview

This section defines the types of safety data that will be collected under this protocol and outlines the procedures for appropriately collecting, grading, recording, and reporting those data.

12.2. Definitions

12.2.1. Adverse Event (AE)

Any untoward or unfavorable medical occurrence associated with the subject's participation in the research, whether or not considered related to the subject's participation in the research (modified from the definition of adverse events in the 1996 International Conference on Harmonization E-6 Guidelines for Good Clinical Practice) (from OHRP "Guidance on Reviewing and Reporting Unanticipated Problems Involving Risks to Subjects or Others and Adverse Events (1/15/07)" http://www.hhs.gov/ohrp/policy/advevntguid.html#Q2)

For this study, an adverse event will include any untoward or unfavorable medical occurrence associated with:

• Study therapy regimen:

Home OIT Dosing

- Food allergy episodes in response to home dosing that are objective Grade 1 or 2 by Modified Bock's Criteria (**APPENDIX 4**) will be recorded on the paper AE CRFs and graded by CTCAE v 4.03 criteria.
- Food allergy episodes in response to home dosing that are Grade 3 by Modified Bock's Criteria (APPENDIX 4) or that are classified as SAEs defined in Section 12.2.3 below will be recorded on the AE/SAE CRF as appropriate and graded by CTCAE v 4.03 criteria.
- Study mandated procedures:

For the procedures below, clinical situations are listed that are considered to be outside the normal range of outcomes and will be recorded as Adverse Events. These situations do not limit an investigator from recording and reporting any other events, associated or not with these procedures as AEs.

Allergen Skin Testing

- Prolonged (>24 hours) itching at test site
- Swelling (> 10 cm) at site of test lasting more than 24 hours
- Nasal allergic symptoms within 30 minutes from the procedure
- Fainting /Vasovagal event within 30 minutes from the procedure

Phlebotomy

- Bruising at phlebotomy site >5 cm with onset within 24 hours of procedure
- Erythema at phlebotomy site >5 cm with onset within 24 hours of procedure
- Infection at phlebotomy site
- Fainting /Vasovagal event within 30 minutes from the procedure

Double-Blind Placebo Controlled Food Challenges

- During DBPCFCs, reactions will be recorded. DBPCFC material is not considered study drug, and as such, reactions will be recorded and reported separately. GI biopsies
 - GI biopsies will be performed on a voluntary subset of participants via an endoscopy. Adverse events will be monitored and documented per the AE listings. Any adverse events related to the procedure or medications used and that meet the criteria for SAE will be reported per the SAE matrix to the FDA and the NIAID medical monitor.

12.2.1.1. Suspected Adverse Reaction (SAR)

Any adverse event for which there is a reasonable possibility that the investigational drug [or investigational study therapy regimen] caused the adverse event. For the purposes of safety reporting, 'reasonable possibility' means there is evidence to suggest a causal relationship between the drug and the adverse event. A suspected adverse reaction implies a lesser degree of certainty about causality than adverse reaction, which means any adverse event caused by a drug (21 CFR 312.32(a)).

12.2.2. Unexpected Adverse Event

An adverse event or suspected adverse reaction is considered "unexpected" if it is not listed in the Investigator Brochure or package insert or is not listed at the specificity, severity or rate of occurrence that has been observed; or, if an Investigator Brochure is not required or available, is not consistent with the risk information described in the general investigational plan or elsewhere in the IND or protocol.

The Principal Investigator will review all adverse events related to skin prick testing, spirometry, DBPCFC, or other study procedures to determine if they are unexpected.

12.2.3. Serious Adverse Event (SAE)

An adverse event or suspected adverse reaction is considered "serious" if it results in any of the following outcomes (21 CFR 312.32(a)):

- 1. Death.
- 2. A life-threatening event: An AE or SAR is considered "life-threatening" if its occurrence places the subject at immediate risk of death. It does not include an AE or SAR that, had it occurred in a more severe form, might have caused death.
- 3. Inpatient hospitalization or prolongation of existing hospitalization.
- 4. Persistent or significant incapacity or substantial disruption of the ability to conduct normal life functions.
- 5. Congenital anomaly or birth defect.
- 6. Important medical events that may not result in death, be life threatening, or require hospitalization may be considered serious when, based upon appropriate medical judgment, they may jeopardize the subject and may require medical or surgical intervention to prevent one of the outcomes listed above.

Elective hospitalizations or hospital admissions for the purpose of conduct of protocol mandated procedures are not to be reported as an SAE unless hospitalization is prolonged due to complications.

12.3. Grading and Attribution of Adverse Events

12.3.1. Grading Criteria

The study physician will grade the severity of adverse events experienced by the study subjects according to the criteria set forth in the National Cancer Institute's Common Terminology Criteria for Adverse Events (CTCAE) v4.03. This document (referred to herein as the NCI-CTCAE manual) provides a common language to describe levels of severity, to analyze and interpret data, and to articulate the clinical significance of all adverse events. The NCI-CTCAE has been reviewed by the Principal Investigator and has been deemed appropriate for the subject population to be studied in this protocol.

Adverse events will be graded on a scale from 1 to 5 according to the following standards in the NCI-CTCAE manual:

Grade 1 = mild adverse event.
Grade 2 = moderate adverse event.
Grade 3 = severe and undesirable adverse event.
Grade 4 = life-threatening or disabling adverse event.
Grade 5 = death.

Events Grade 1 or higher will be recorded on the appropriate paper AE case report form for this study.

Anaphylaxis will be defined when there is: 1) Symptomatic bronchospasm, with or without urticaria, with parenteral intervention indicated with edema and hypotension; or 2) Life-threatening consequences with urgent intervention indicated.

12.3.2. Attribution Definitions

The relationship, or attribution, of an adverse event to the study therapy regimen or study procedure(s) will initially be determined by the site investigator/study physician and recorded on the appropriate AE/SAE paper case report form and according to SUSAR guidelines

(http://www.fda.gov/downloads/Drugs/.../Guidances/UCM227351.pdf)Final determination of attribution of SAE for safety reporting will be determined by DAIT/NIAID.

For additional information and a printable version of the NCI-CTCAE manual, consult the NCI-CTCAE web site: http://ctep.cancer.gov/reporting/ctc.html.

12.4. Collection and Recording of Adverse Events

12.4.1. Collection Period

Adverse events will be collected from the time of consent until a subject completes study participation or until 30 days after he/she prematurely withdraws (without withdrawing consent) or is withdrawn from the study.

12.4.2. Collecting Adverse Events

Adverse events (including SAEs) may be discovered through any of these methods:

- Observing the subject.
- Interviewing the subject [e.g., using a checklist, structured questioning, diary, etc.] .
- Receiving an unsolicited complaint from the subject.

12.4.3. Recording Adverse Events

Throughout the study, the investigator will record adverse events and serious adverse events as described previously (Section 12.2, *Definitions*) on the appropriate AE/SAE paper CRF regardless of the relationship to study therapy regimen or study procedure.

Once recorded, an AE/SAE will be followed until it resolves with or without sequelae, or until 30 days after the subject prematurely withdraws (without withdrawing consent)/or is withdrawn from the study, whichever occurs first.

